12.1 Efficacy Variables

12.1.1 Primary Endpoint

The primary endpoint is the time from randomization to relapse in the double-blind period.

12.1.2 Key Secondary Endpoint

The key secondary endpoint is time from randomization to discontinuation from the double-blind period for any reason (other than termination of the study by the sponsor).

12.1.3 Exploratory Study Endpoints

Change from double-blind Baseline on the following:

- Scale for the Assessment of Positive Symptoms-Hallucinations+Delusions (SAPS-H+D) score
- SAPS Hallucinations domain score
- SAPS Delusions domain score
- Clinical Global Impression-Severity (CGI-S)-dementia-related psychosis
- Zarit Burden Interview (ZBI) score
- Karolinska Sleepiness Scale (KSS) score
- EQ-5D VAS score and EQ-5D-5L descriptive system
- Clinical Global Impression-Improvement (CGI-I)-dementia-related psychosis

12.2 Adjustment for Covariates

For time-to-event variables analyzed using the Cox regression model, region and designated dementia subtype (as defined by randomization strata) will be included as covariates as described in [Section 13](#).

For continuous variables (except CGI-I) analyzed using a mixed model for repeated measures (MMRM) or an analysis of covariance (ANCOVA), the Baseline value of the endpoint being analyzed, region, and designated dementia subtype will be included as covariates as described in [Section 13.3](#). For CGI-I, the Baseline CGI-S score, region, and designated dementia subtype will be included as covariates in the MMRM and ANCOVA analyses.

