3.4 Double-blind Period (up to 26 Weeks)

Randomization will occur at the double-blind Baseline visit (Week 12). Subjects will be randomly assigned 1:1 to continue their pimavanserin dose (34 mg or 20 mg) or matching placebo.

The protocol-defined relapse criteria for dementia-related psychosis are designed to identify subjects with an impending relapse or relapse of psychosis:

- Subject experiences a $\geq 30\%$ increase (worsening) from Week 12 (double-blind Baseline) on the SAPS-H+D Total Score AND has a CGI-I score of 6 (much worse) or 7 (very much worse), relative to the double-blind Baseline¹; OR
- Subject is treated with an antipsychotic (other than pimavanserin) for dementia-related delusions and/or hallucinations; OR
- Subject stops study drug or withdraws from study for lack of efficacy, (as reported by the subject or study partner/caregiver) or the Investigator discontinues study drug due to lack of efficacy; OR
- Subject is hospitalized for worsening dementia-related psychosis

Relapse criteria will be assessed weekly for the first 2 weeks after randomization (Weeks 13 and 14), every 2 weeks until Week 26, and every 4 weeks through Week 38. Relapse criteria may also be evaluated at unscheduled visits. Any subject who meets any of the relapse criteria after randomization will be withdrawn from study drug and enter the safety follow-up period of the study.

All subjects who discontinue the study between randomization and Week 38 should complete an ET visit, if possible, and an independent adjudication committee (IAC) will review those cases that occurred before the study discontinuation date to determine if protocol-defined relapse criteria were met.

Pharmacokinetic samples will be collected at Weeks 13, 22, and 38/EOT. Pharmacokinetic samples will also be collected, if possible, at any ET visit or the visit immediately following any SAE or following an AE leading to discontinuation.

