9.5.1 Primary Efficacy Analyses

The time from randomization to relapse in the double-blind period will be compared between treatment groups using a Cox regression model with effects for treatment group, dementia subtype, and region. The nominal p-value, hazard ratio, and 95% confidence interval will be reported. Subjects who discontinue early or complete the study without having experienced a

relapse event will be censored at the time of last assessment for relapse. The primary analysis will be based on adjudicated relapse events ([Section 9.5.7](#)).

A sensitivity analysis will be performed based on the Investigator assessment of relapse. Additional sensitivity analyses to assess the potential impact of informative censoring will be specified in the Statistical Analysis Plan.

Kaplan-Meier curves of time from randomization to relapse will be presented for each treatment group. In addition, Kaplan-Meier estimates of the proportion of subjects who relapse along with pointwise 95% confidence intervals will be provided for the 26-week double-blind period.

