5.2.2 Double-blind Baseline

Double-Blind Baseline is defined as the last non-missing assessment, including those from repeated and unscheduled measurements, on or before the date of first dose of double-blind study drug.

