8.2 Disease Characteristics

Disease characteristics will be summarized descriptively for the Open-label Safety Analysis Set, ITT Analysis Set, Double-blind Safety Analysis Set, and Per-protocol Analysis Set.

Dementia subtype: Alzheimer's disease, FTD spectrum disorders, vascular dementia, Parkinson's disease dementia, and dementia with Lewy bodies; and dementia severity will be presented as a categorical variable. Open-label and double-blind Baseline MMSE total score, SAPS-H+D total score, ZBI score, KSS score, EQ-5D VAS score, and CGI-S score will be presented as continuous variables. In addition, open-label and double-blind Baseline CGI-S score will be presented as categorical variables using categories of 1 to 7.

Neuropsychiatric history will be summarized descriptively for continuous and categorical variables.

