The treatment effect will be measured by the HR. The pimavanserin group includes all subjects taking pimavanserin irrespective of the dose (20 mg or 34 mg). The time from randomization to relapse in the double-blind period will be compared between treatment groups using a Cox regression model with effects for treatment group, designated dementia subtype (Alzheimer's disease or FTD spectrum disorders, Vascular dementia, Parkinson's disease dementia or dementia with Lewy bodies), and region (levels: North America, Western Europe, Eastern Europe, Asia Pacific, Latin America) as covariates in the model. A robust sandwich-type variance method will be applied to compute the variance of the estimated HR (Lin et. al., 1989), which can be computed as $\mathbf{D}'\mathbf{D}$ where \mathbf{D} is the matrix of DFBETA residuals. The Cox exact discrete method will be used to compute the partial likelihood function to account for tied relapse times. The estimated HR, SE, 95% confidence interval, and p-value obtained from the Cox regression model will be presented. The algorithm for censoring of subjects who discontinued early, completed the study without having experienced a relapse event, or were ongoing at the time of database cutoff is described in [Section 5.2.3](#). The number and percentage of subjects having the following possible reasons for censoring will be tabulated for each treatment group:

- Completed Week 26 without relapse;
- Prematurely discontinued prior to Week 26, for reasons other than termination of the study by the sponsor;
- Ongoing at the time of database cutoff (for the interim analysis only);
- Termination of the study by the sponsor (for the final analysis only).

Kaplan-Meier curves of time from randomization to relapse will be presented for each treatment group. In addition, Kaplan-Meier estimate of median survival (relapse free time) and probability estimates at the double-blind Weeks 4, 8, 12, 18, and 26 along with pointwise 95% confidence intervals will be provided. The confidence intervals will be calculated using a log-log transformation and Greenwood's variance formula.

The number and percentage of subjects meeting at least one of the following relapse criteria will be tabulated for each treatment group:

- Experienced a $\geq 30\%$ increase (worsening) on the SAPS-H+D total score AND has a CGI-I score of 6 (much worse) or 7 (very much worse), relative to the double-blind Baseline;

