13.1.1 Deviations From Non-Informative Censoring

One of the assumptions underlying the primary analysis is that the censoring mechanism is non-informative. In order to assess the sensitivity of the primary analysis to deviations from this assumption, a reference-based multiple imputation method will be used (Lu et. al., 2015). Subjects who don't relapse but who discontinue from the study prior to the Week 26 assessment, for any reason other than termination of the study by the sponsor, will have time to relapse values imputed conditionally on their observed censored values. Censoring due to completion of the 26 week double-blind period, study being terminated by the sponsor or ongoing at the time of the interim analysis datacut (for the interim analysis only), will be treated as non-informative and no imputation will be performed for these subjects. The

imputation algorithm will be based on the assumption that the risk of relapse (i.e. hazard rate) for pimavanserin subjects who prematurely discontinue is the same as that for placebo subjects. If the imputed event time exceeds the applicable cutoff date for a planned analysis, or the date corresponding to Week 26 for the subject, whichever comes first, the time-to-event will be right censored at the earlier of the two dates. Random number seeds of 201938 and 202075 will be used for the posterior draw of model parameters from the imputation model and for imputation of censored event times, respectively. A total of 1000 imputed datasets will be created.

The imputation model will be a Cox regression model with piecewise exponential baseline hazards fit to the ITT Analysis Set with treatment, designated dementia subtype, and region as covariates. A noninformative improper prior for the baseline hazard parameters and an improper uniform prior for the regression coefficients will be assumed. For the piecewise constant baseline hazards, the post-baseline follow-up time axis will be partitioned into 2 disjoint intervals, where the interval cut-points will be such that there will be a similar amount of relapse events in each interval. Sampling of model parameters will set the burn-in to 200 and every 10th sample will be kept. [REDACTED]

[REDACTED]

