The same Cox regression model as described in [Section 13.1](#) will be used for each of the sensitivity analyses. The results will be presented in a summary table similar to that described for the primary efficacy analysis. The estimated HRs with corresponding 95% CIs from the primary efficacy analysis and the sensitivity analyses will be presented in a forest plot.

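### The primary relapse model adjusts only for the randomization strata; prespecifying the double-blind Baseline SAPS-H+D score as well costs little and may add power

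*SAP*

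**What the plan says.** Protocol 9.5.1 compares time to relapse "using a Cox regression model with effects for treatment group, dementia subtype, and region". SAP 13.1 matches it, "using a Cox regression model with effects for treatment group, designated dementia subtype" and region, and SAP 12.2 states the general rule: "region and designated dementia subtype (as defined by randomization strata) will be included as covariates".

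The supporting analyses carry the same terms. The imputation model in SAP 13.1.1 is fitted "with treatment, designated dementia subtype, and region as covariates", and so are the Cox models run on the 1000 imputed datasets. SAP 13.1.2 says the model of 13.1 "will be used for each of the sensitivity analyses". The key secondary endpoint (13.2) uses it too. Baseline SAPS-H+D is not among the subgroups in 12.5.1.

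The score itself is available. SAPS-H+D is scheduled at Week 12, where it is needed to judge response before randomization. SAP 8.2 tabulates "Open-label and double-blind Baseline MMSE total score, SAPS-H+D total score" and other scores. The exploratory MMRM and ANCOVA models do adjust for a Baseline score.

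**The concern.** In Protocol 3.4 the first relapse criterion is a rise of at least 30% "on the SAPS-H+D Total Score AND has a CGI-I score of 6 (much worse) or 7 (very much worse"), both judged against double-blind Baseline. The Baseline score therefore fixes how many points a subject must gain to meet the SAPS part. A link between that score and time to relapse is plausible, although its direction and size cannot be known in advance.

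Two things are at stake if the score is prognostic. The strata-only model gives up some power. A chance difference between the arms in Baseline score also moves the estimated hazard ratio. The SAP 8.2 table would show such a difference, but no prespecified analysis corrects for it, and an adjusted model added after unblinding would be post hoc.

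**Working it through.** **Inputs from the plan** (Protocol 9.3 and 9.5.8; SAP 3.4 and 16.1): relapse over 26 weeks 60% on placebo and 35% on pimavanserin; dropout 25%; 75 events; 89 per arm; final two-sided level 0.0479.

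**1. The plan's own sizing reproduces.**
- Hazard ratio: ln(0.65)/ln(0.40) = 0.470.
- Events for 90% power with the SAP 16.1 boundary: 74.3, rounded up to 75.
- Event probabilities with competing exponential dropout: 0.533 and 0.307, mean 0.420. Then 75/0.420 is about 178.6, against 178 planned.
- Power at 75 events: Φ(√(75/4) × |ln 0.470| − 1.978) = 0.901.

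So the design meets its target without the extra covariate.

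**2. How Baseline sets the SAPS cut-off.** The total is an integer from 0 to 100 (SAP 5.2.5). The smallest rise of at least 30% is:

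| Baseline | Points needed |
|---|---|
| 0 | any rise (footnote to Protocol 3.4) |
| 1 to 3 | 1 |
| 7 to 10 | 3 |
| 20 | 6 |
| 35 | 11 (10.5 rounded up) |

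**3. Power without and with the score.** 8,000 simulated trials per row, 89 per arm, with marginal relapse rates held at 60% and 35%. Relapse times are exponential, the score is standard normal, dropout is 25% and follow-up ends at 26 weeks, giving about 75 events. The Cox model has treatment, 2 subtype and 4 region terms, and the robust variance of SAP 13.1 is tested at 0.0479. Assumed, not in the documents: the prognostic strength and the strata shares (subtype 65/10/25%, region 35/20/25/5/15%).

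| Assumed HR per SD | Power without | Power with | Gain (points) | Mean HR without / with |
|---|---|---|---|---|
| 1.0 | 87.9% | 87.7% | -0.2 | 0.459 / 0.457 |
| 1.25 | 88.9% | 89.3% | +0.4 | 0.456 / 0.449 |
| 1.5 | 88.6% | 91.0% | +2.4 | 0.455 / 0.435 |
| 2.0 | 90.3% | 95.5% | +5.3 | 0.448 / 0.399 |
| U-shaped effect | 88.6% | 88.4% | none | not reported |

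The Monte Carlo standard error is about 0.35 points per power figure, and gains are taken before rounding. A separate simulation (4,000 trials per setting) gave 87.9 to 87.8% when the score was not prognostic, 88.7 to 91.0% at a log hazard ratio of 0.4 per SD, and 88.9 to 93.5% at 0.6.

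**4. Type I error, one-sided.**
- Final analysis, nominal 2.4%: the simulation in step 3, with both arms at 60% relapse, gave 2.4 to 2.7% without the term and 2.6 to 2.8% with it (SE 0.18).
- A run stopped at exactly 75 events gave 2.6 to 2.8% without and 2.9 to 3.2% with (SE about 0.26).
- A larger run at about 76 to 77 events (18,000 to 20,000 trials, SE about 0.08) gave 2.66/2.69% for a non-prognostic score and 2.31/2.39% at log hazard ratio 0.4. The term therefore adds less than 0.1 point.
- Interim at 38 events, nominal 0.27%: 0.30 to 0.35% without, 0.26 to 0.29% with.

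**5. Chance imbalance.** The 95% limit for the standardized difference at 89 per arm is 1.96 × √(2/89) = 0.29 SD. The unadjusted hazard ratio is multiplied by (HR per SD)^0.29, which is 1.07, 1.13 and 1.23 at 1.25, 1.5 and 2.0. Simulation gave 1.06, 1.12 and 1.20. With the score in the model the factor was 0.99 to 1.00.

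**The case against.** The strongest reply is that this is a preference. Protocol and SAP agree with each other, adjusting for the stratification factors is valid, and the sizing works without the term. The benefit rests on a prognostic strength that no document supplies. A low Baseline makes the SAPS cut-off easier to reach, while a high one may mark more residual illness. These forces could cancel or give a non-monotone relation that one linear term misses. The cut-off is only part of one criterion among four. The score is bounded at 0 in subjects selected for response, so a normal covariate with continuous relapse times is idealised. An imbalance of 0.29 SD against the drug has about a 2.5% chance, and the test's error rate already allows for it. The target becomes a hazard ratio conditional on Baseline. Events per parameter fall from 38/7 = 5.4 to 38/8 = 4.8 at the interim.

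Much of this stands: the plan contains no error, the gain may be nil, and the hazard ratio does change meaning. The objection about idealised data was tested with a skewed integer score with a floor at 0 and relapse grouped to visits. Power without and with the term was then 88.2/88.2% (not prognostic), 88.6/91.3% (HR 1.5 per SD), 88.8/89.8% (inverse effect) and 88.4/89.1% (non-monotone effect). One-sided null rejection with and without the term was within 0.1 point. No setting showed a meaningful loss.

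**Conclusion.** The point holds as a recommended improvement to a valid plan, with medium confidence. No prespecified time-to-relapse analysis uses the double-blind Baseline SAPS-H+D score, and the documents give no reason for leaving it out.

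The likely effect runs from no gain, if the score is unrelated to relapse or its effect is strongly U-shaped, to about 2 points of power at a hazard ratio of 1.5 per SD and about 5 at 2.0. The prespecified term also removes almost all of the shift from a chance imbalance. The case rests on asymmetry: the simulated cost is within Monte Carlo error and the possible gain is modest but real. The power figures cover the final test alone, without the interim look.

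**What to change.** Before unblinding for the interim analysis, which is the deadline Protocol 9.1 sets for SAP approval, amend SAP 12.2 and 13.1 along these lines:

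> The Cox model for time to relapse will contain treatment, the two stratification factors as used at randomization, and the double-blind Baseline SAPS-H+D total score as a continuous linear term. For a randomized subject who took no double-blind dose, the score used is the latest non-missing one up to and including the day of randomization.

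The second sentence is needed because SAP 5.2.2 defines this Baseline as the last value "on or before the date of first dose of double-blind study drug", while the ITT set is everyone randomized.

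- Add the term to the imputation model in 13.1.1 and to the Cox fits of the imputed datasets. State whether it stays if the model falls back to treatment only because of sparse covariates.
- Keep the strata-only model as a sensitivity analysis in 13.1.2.
- Say in 13.2 whether the key secondary model carries the term, since that section inherits the primary model. It is optional there, because the cut-off acts on discontinuation only through relapse.
- Record the change in SAP Section 20, which now declares no deviations, and align Protocol 9.5.1 and the synopsis.

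The cost is document changes and one more parameter, with no new data. The downsides are the assumed log-linear form and a hazard ratio read conditional on Baseline. If the sponsor prefers to leave the primary model alone, the least worth doing is one prespecified supportive Cox analysis with this covariate in 13.1.2. That would give any observed imbalance a prespecified answer, but it would bring no power to the primary test.

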12.3 Handling of Informative Censoring

The primary time-to-event analysis using the Cox regression model assumes the censoring times are independent of the event times (i.e., the censoring is non-informative). The robustness of the primary analysis results to certain deviations from non-informative censoring will be evaluated using a reference-based multiple imputation method (Lu et al., 2015). Further details are provided in Section 13.1.1.

12.4 Multiple Comparisons/Multiplicity

A hierarchical testing procedure will be used to control the overall type I error rate for the primary and key secondary efficacy endpoints. Hypothesis testing will occur in the following sequential order:

1. Primary endpoint
2. Key secondary endpoint

Adjustment of the analyses of the primary and key secondary efficacy endpoints to account for the interim efficacy analysis is described in Section 16.

12.5 Examination of Subgroups

12.5.1 Double-Blind Period

Treatment comparisons will be made with respect to the primary and key secondary efficacy variables using the Cox regression described in Sections 13.1 and 13.2 for the following subgroups:

- Region (North America, Western Europe, Eastern Europe, Asia Pacific, Latin America)
- Designated dementia subtype (Alzheimer's disease or FTD spectrum disorders, Vascular dementia, Parkinson's disease dementia or dementia with Lewy bodies)
- Parkinson's disease dementia (yes)
- Alzheimer's disease (yes)
- FTD spectrum disorders (yes)

- Dementia with Lewy bodies (yes)
- Age group (<75 or ≥75 years old)
- Sex (male or female)
- Primary race (white or non-white)
- Screening dementia severity (mild, moderate, severe)
- OL Baseline antidementia medication (memantine and/or acetylcholinesterase inhibitors) use (yes, no)
- Antipsychotic use within 14 days of screening (yes, no).
- OL Baseline MMSE (<18, ≥18)

For each subgroup, Kaplan-Meier curves of time to relapse and time to discontinuation from the double-blind period for any reason (other than termination of the study by the sponsor) will be presented for each treatment group. The hazard ratios with corresponding 95% CIs obtained from the Cox regression model for each subgroup will be presented in forest plots for the primary and key secondary efficacy variables.

12.5.2 Open-Label Period

For each subgroup listed above, the number and percentage of subjects in the Open-label Safety Analysis Set who met the response criteria for randomization will be summarized.

SAPS-H+D, SAPS-H, and SAPS-D assessments from the open-label period for the Open-label Safety Analysis Set will be descriptively summarized ([Section 13.3.2](#)) by designated dementia subtype.

13 METHODS OF EFFICACY ANALYSES

13.1 Primary Efficacy Analysis

The primary efficacy endpoint is the time from randomization to relapse in the double-blind period. The hypotheses are stated in terms of the hazard ratio, $HR = \lambda_{PIM} / \lambda_{PBO}$, where λ_{PIM} and λ_{PBO} denote the hazard rates of relapse for the pimavanserin group (20 mg and 34 mg combined) and the placebo group, respectively.

The null hypothesis for the primary efficacy endpoint is: $HR = 1$

The alternative hypothesis for the primary efficacy endpoint is: $HR \neq 1$

The primary efficacy analysis will be based on adjudicated relapse events determined by the IAC for the ITT Analysis Set. If the study is stopped at the interim analysis, the primary efficacy analysis will be based on the interim analysis dataset (see [Section 16](#) for additional details). If the study is not stopped at the interim analysis, the primary analysis will be based on all data collected up until the study discontinuation date; data collected after the study discontinuation date will not be used in the primary analysis.

The treatment effect will be measured by the HR. The pimavanserin group includes all subjects taking pimavanserin irrespective of the dose (20 mg or 34 mg). The time from randomization to relapse in the double-blind period will be compared between treatment groups using a Cox regression model with effects for treatment group, designated dementia subtype (Alzheimer's disease or FTD spectrum disorders, Vascular dementia, Parkinson's disease dementia or dementia with Lewy bodies), and region (levels: North America, Western Europe, Eastern Europe, Asia Pacific, Latin America) as covariates in the model. A robust sandwich-type variance method will be applied to compute the variance of the estimated HR (Lin et. al., 1989), which can be computed as $\mathbf{D}'\mathbf{D}$ where \mathbf{D} is the matrix of DFBETA residuals. The Cox exact discrete method will be used to compute the partial likelihood function to account for tied relapse times. The estimated HR, SE, 95% confidence interval, and p-value obtained from the Cox regression model will be presented. The algorithm for censoring of subjects who discontinued early, completed the study without having experienced a relapse event, or were ongoing at the time of database cutoff is described in [Section 5.2.3](#). The number and percentage of subjects having the following possible reasons for censoring will be tabulated for each treatment group:

- Completed Week 26 without relapse;
- Prematurely discontinued prior to Week 26, for reasons other than termination of the study by the sponsor;
- Ongoing at the time of database cutoff (for the interim analysis only);
- Termination of the study by the sponsor (for the final analysis only).

Kaplan-Meier curves of time from randomization to relapse will be presented for each treatment group. In addition, Kaplan-Meier estimate of median survival (relapse free time) and probability estimates at the double-blind Weeks 4, 8, 12, 18, and 26 along with pointwise 95% confidence intervals will be provided. The confidence intervals will be calculated using a log-log transformation and Greenwood's variance formula.

The number and percentage of subjects meeting at least one of the following relapse criteria will be tabulated for each treatment group:

- Experienced a $\geq 30\%$ increase (worsening) on the SAPS-H+D total score AND has a CGI-I score of 6 (much worse) or 7 (very much worse), relative to the double-blind Baseline;
- Treated with an antipsychotic (other than pimavanserin) for dementia-related delusions and/or hallucinations;
- Stopped study drug or withdrew from study for lack of efficacy, (as reported by the subject or study partner/caregiver) or the Investigator discontinues study drug due to lack of efficacy;
- Hospitalized for worsening dementia-related psychosis.

The number and percentage of subjects meeting each of the relapse criteria will be tabulated. A subject who meets more than one of the relapse criteria will be counted once for each of the relapse criteria that were met.

